4.0 Patient Selection

4.1. Inclusion Criteria

- 4.1.1 18 years of age or older
- 4.1.2 A diagnosis of renal AML > 3 cm confirmed on pre-enrollment DCE MRI. A previous diagnosis or treatment of a different AML lesion is allowed.
- 4.1.3 ECOG Performance Status 0 or 1
- 4.1.4 Patients must have normal organ and marrow function as defined below:
 - Absolute neutrophil count > 1,500/mcL

- Hemoglobin \geq 10 g/dL
 - Platelets $>$ 100,000/mcL
 - AST/ALT (SGOT/SGPT) $<$ 2.5 X ULN
 - Total bilirubin \leq 2.0mg/dL
 - Renal Function eGFR $>$ 30 mL/min via calculated creatinine clearance
 - Fasting serum cholesterol \leq 300 mg/dL **OR** \leq 7.75 mmol/L
 - Fasting triglycerides \leq 300 mg/dL or \leq 1.71 mmol/L.
- 4.1.5 Ability to understand and willingness to sign a written informed consent and HIPAA consent document

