4.2. Exclusion Criteria

- 4.2.1 History of tuberous sclerosis, LAM or any active malignancy
- 4.2.2 Active treatment with any other investigational agents
- 4.2.3 Administration of any investigational drug within 30 days or 5 half-lives, whichever is longer, preceding the first dose of study treatment.
- 4.2.4 Concurrent therapy given to treat cancer
- 4.2.5 Patients must not have received any prior treatment for AML
- 4.2.6 Diagnosis of any other malignancy within 3 years prior to registration, except for adequately treated basal cell or squamous cell skin cancer, or carcinoma in situ of the breast or of the cervix or melanoma in-situ or low grade (Gleason 6 or below) prostate cancer on surveillance with no plans for treatment intervention (eg, surgery, radiation or castration).
- 4.2.7 Clinically significant gastrointestinal abnormalities that may increase the risk for gastrointestinal bleeding including, but not limited to:
- Active peptic ulcer disease
 - Inflammatory bowel disease (e.g. ulcerative colitis, Crohn's disease), or other gastrointestinal conditions with increased risk of perforation.
 - History of abdominal fistula, gastrointestinal perforation, or intra-abdominal abscess within 28 days prior to beginning study treatment
- 4.2.8 Active diarrhea of any grade.
- 4.2.9 Clinically significant gastrointestinal abnormalities that may affect absorption of investigational product including, but not limited to:
- Malabsorption syndrome
 - Major resection of the stomach or small bowel resulting in dumping syndrome or clinical signs of malabsorption

- 4.2.10 Active or prior history of human immunodeficiency virus (HIV), hepatitis B, or hepatitis C (screening for all three is mandatory prior to study)
- 4.2.11 Presence of any active or ongoing infection.
- 4.2.12 Any known uncontrolled underlying pulmonary disease by history, physical exam or if applicable PFTs (e.g. FEV1 or DLCO 50% or less of predicted OR O2 saturation 88% or less at rest on room air).
- 4.2.13 History of any one or more of the following cardiovascular conditions within the past 6 months:
- Cardiac angioplasty or stenting
 - Myocardial infarction
 - Unstable angina
 - Coronary artery bypass graft surgery
 - Symptomatic peripheral arterial vascular disease
- 4.2.14 History of Class III or IV congestive heart failure, as defined by the New York Heart Association Classification of Congestive Heart Failure. See Appendix I for NYHA Classification Table.

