- 4.2.15 History of cerebrovascular accident including transient ischemic attack (TIA), pulmonary embolism or untreated deep venous thrombosis (DVT) within the past 6 months.
Note: Patients with recent DVT who have been treated with therapeutic anticoagulation agents for at least 6 weeks are eligible as long as their INR is stable and within inclusion criteria per 4.1.4
- 4.2.16 Corrected QT interval (QTc) > 480 milliseconds as corrected by the Fridericia formula
- 4.2.17 Poorly controlled hypertension, defined as systolic blood pressure (SBP) of ≥ 140 mmHg or diastolic blood pressure (DBP) of ≥ 90 mmHg.
Note: Screening/Baseline blood pressure (BP) must be assessed with three measurements at approximately 2-minute intervals. The mean SBP / DBP values from the three readings must be $< 140/90$ mmHg in order for a subject to be eligible for the study. If the subject's initial screening SBP/DBP is $\geq 140/90$ mmHg, initiation or adjustment of antihypertensive medication(s) is permitted in an attempt to control the subject's BP level to below $140/90$ mmHg. Optimal blood pressure control must be achieved before registration and monitored.
- 4.2.18 Evidence of active bleeding or bleeding diathesis
- 4.2.19 Patients must not have uncontrolled diabetes mellitus (defined by a Hgb A1c > 8) obtained within 14 days prior to registration. Optimal glucose control (Hgb A1c ≤ 8) must be achieved before registration and monitored during protocol treatment

- 4.2.20 Unable or unwilling to discontinue use of prohibited medications within 14 days prior to randomization and while on treatment:
- No chronic treatment with systemic steroids or another immunosuppressive agent. Topical or inhaled corticosteroids are allowed.
 - Growth factors (e.g. G-CSF, G-GM-CSF, erythropoietin, platelets growth factors etc.) are not to be administered prophylactically but may be prescribed by the treating physician for rescue from severe hematologic events.
 - Live vaccines must not be administered to patient due to immunosuppressant potential of everolimus.

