 - Drugs known to be strong inhibitors or inducers of CYP3A4 must not be administered. Drugs or substances known to be moderate inhibitors or inducers of CYP3A should be avoided if possible or used subject to caution as these can alter everolimus metabolism. Co-administration with strong or moderate inhibitors of P-glycoprotein (PgP) should be avoided if possible, or used subject to caution Seville orange, star fruit, grapefruit and their juices affect P450 and PgP activity. Concomitant use should be avoided.
- 4.2.21 Have a known immediate or delayed hypersensitivity reaction or idiosyncrasy to drugs chemically related to everolimus that in the opinion of the investigator contraindicates their participation.
- 4.2.22 Prior or current use of systemic anti-VEGF inhibitors, cytokines or mTOR inhibitors (e.g. interferon, interleukin 2).
- 4.2.23 Patients with Child-Pugh A-C liver disease (See Appendix II: Child-Pugh Criteria)
- 4.2.24 Pregnant or nursing (lactating) women
- 4.2.25 Women of child-bearing potential (WOCBP), defined as all women physiologically capable of becoming pregnant, must use highly effective methods of contraception during the study and 8 weeks after stopping treatment. Highly effective contraception methods include total abstinence, male partner sterilization (with post-vasectomy documentation of the absence of sperm in the ejaculate), or a combination of **any two** of the following:
- Use of oral, injected or implanted hormonal methods of contraception
 - In case of use of oral contraception, women should have been stable on the oral agent before taking study treatment.
 - Placement of an intrauterine device (IUD) or intrauterine system (IUS)
 - Barrier methods of contraception: condom or occlusive cap (diaphragm or cervical/vault caps) with spermicidal foam/gel/film/cream/ vaginal suppository

Women are considered to be physiologically capable of becoming pregnant unless:

- They have had 12 months of natural (spontaneous) amenorrhea with an appropriate clinical profile (e.g. age appropriate, history of vasomotor symptoms);
- They have had surgical bilateral oophorectomy (with or without hysterectomy) or tubal ligation at least six weeks prior to randomization.
 - In the case of oophorectomy alone, only when the reproductive status of the woman has been confirmed by follow up hormone level assessment is she considered not of child-bearing potential.

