4.2.26 Male patients whose sexual partner(s) are WOCBP must agree to use adequate contraception as defined above during the study and for 8 weeks after the end of treatment. Condom use is required by all male patients in order to prevent delivery of the drug via seminal fluid.

4.2.27 Any serious and/or unstable pre-existing medical, psychiatric, or other condition that could interfere with subject's safety, provision of informed consent, or compliance to study procedures. Patients with low risk prostate and bladder cancer will be excluded (use AUA guidelines for bladder patients).

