8.0 Study Calendar

	Screening ^A	Day 1 of Cycles 1, 3, and 5 ^H	Day 1 of Cycles 2, 4, and 6 ^H	Cycle 5 Day 1 ^H	Cycle 6 Day 28 ^H	Off Treatment	12 Month Follow-up ^H
Informed Consent	X						
Medical History	X						
Concurrent Medications	X	X	X			X	
Height	X						
Weight	X	X	X			X	
Physical exam	X	X	X			X	
Vital signs ^B	X	X	X			X	
ECOG Performance Status	X	X	X			X	
Serum chemistry ^C	X	X	X			X	
FKSI QOL Assesment	X	X	X			X	X
CBC w/diff, plts	X	X	X			X	
Fasting serum cholesterol & Triglycerides & Hgb A1c	X	X				X	
EKG	X						
Hepatitis B, Hepatitis C & HIV Screening ^D	X						
Tumor Measurements	X			X	X		X
Optional Correlative Tissue Collection		X ^E	X ^F				
Optional Correlative Serum Collection		X ^E		X	X		X
Serum Pregnancy Test ^G	X						
Urine or Serum Pregnancy Test ^G		X	X			X	
Adverse Event Assessment		X	X				

- A: Screening H&P, EKG and all labs must be ≤ 14 days prior to registration. Tumor measurements and radiologic evaluations must be ≤ 30 days prior to registration. Pre-study assessments may be used for cycle 1 day 1
- B: Screening blood pressure must be assessed with three measurements at approximately 2-minute intervals.
- C: Serum chemistry includes Albumin, alkaline phosphatase, total bilirubin, bicarbonate, BUN, calcium, chloride, creatinine, fasting glucose, LDH, phosphorus, potassium, total protein, SGOT [AST], SGPT [ALT], sodium, glucose.
- D: Screening for Hepatitis B will include, HBsAg, HBsAb, and HBc Ab. A positive HBsAb result in patients who have received prior HBV vaccination will not lead to exclusion from the study as long as HBsAg is negative. Screening for Hepatitis C will be via Hepatitis C antibody. If positive confirmation with quantitative RNA PCR will be done.
- E: If archival tissue is available from a previous renal lesion biopsy, unstained slides will be collected as detailed in 5.5. Correlative blood and tissue for this timepoint will be collected at Cycle 1 Day 1 only.
- F: If a percutaneous intervention or surgical intervention is performed during the study, tissue will be collected for further a analysis as detailed in 5.5
- G: Women of Childbearing Potential Only. Serum pregnancy test at time of screening must be completed **<72 hours** before registration
- H: All study visits have a window of +/- 5 days. Ensure that patients are given enough study drug to last until their next visit if scheduled more than 28 days from start of a cycle.

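### Two eligibility criteria need reconciling: 4.1.2 and 4.2.5 conflict as written on prior AML treatment, and the two units of the triglyceride limit in 4.1.4 differ about two-fold

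*Combined protocol and SAP*

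**What the plan says.** All references are to the combined protocol and SAP.

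- **Prior AML treatment.** Section 4.1.2 requires a renal AML above 3 cm on the pre-enrollment DCE-MRI and adds: "A previous diagnosis or treatment of a different AML lesion is allowed". Section 4.2.5 states: "Patients must not have received any prior treatment for AML". It makes no exception for another lesion. Section 4.2.22 separately excludes "Prior or current use of systemic anti-VEGF inhibitors, cytokines or mTOR inhibitors".
- **Triglycerides.** Section 4.1.4 gives the fasting triglyceride limit as 300 mg/dL or 1.71 mmol/L. The line above gives fasting cholesterol as 300 mg/dL or 7.75 mmol/L. The Study Calendar (8.0) has a screening entry for every patient in the row "Fasting serum cholesterol & Triglycerides & Hgb A1c".
- **INR (minor).** The note to 4.2.15 admits patients with a recently treated DVT "as long as their INR is stable and within inclusion criteria per 4.1.4".
- **Prostate cancer (minor).** Section 4.2.6 exempts "low grade (Gleason 6 or below) prostate cancer on surveillance with no plans for treatment intervention" from the exclusion for other malignancies. Section 4.2.27 says: "Patients with low risk prostate and bladder cancer will be excluded". Section 4.2.1 also excludes "History of tuberous sclerosis, LAM or any active malignancy", without stating exceptions.

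**The concern.** Eligibility criteria should give one answer for one patient. Here a patient whose other AML was treated earlier is allowed by one criterion and excluded by another. A patient with moderately raised triglycerides may be eligible or not, depending on the unit and on how the word *or* is read.

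What is at stake is who enters the trial and whether screening decisions are consistent. Patients with more than one AML are foreseen, because Section 3.0 follows the summed volume of all target AMLs. Section 1.1 describes surgery or embolization as current standard care for larger sporadic AMLs, so earlier local treatment of another lesion is a foreseeable history. Section 12.2 plans to add 2 to 4 sites, so more investigators would screen from this text. Under Section 3.0, everyone who takes one dose is analysed and dropouts are not replaced, so a patient enrolled in error stays among the 43.

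**Working it through.** **1. Prior AML treatment (no arithmetic applies).** Take a patient with a study AML above 3 cm that has never been treated, and a different AML that was embolized earlier.

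- Under 4.1.2 the earlier treatment is no bar.
- Under the literal text of 4.2.5 the patient is excluded, because the criterion covers all prior AML treatment and names no lesion.
- If every criterion binds, the treatment part of the permission in 4.1.2 has no effect.
- If 4.2.5 is read as covering only the study lesion, the two agree, but that limit has to be supplied by the reader.
- Because 4.2.22 already excludes prior systemic anti-VEGF, cytokine and mTOR therapy, the disputed group is mainly patients with earlier local treatment.

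**2. Triglyceride limit.** Inputs from 4.1.4: 300 mg/dL and 1.71 mmol/L (triglycerides); 300 mg/dL and 7.75 mmol/L (cholesterol). The documents give no conversion, so the molar mass M (g/mol) is an assumption. The formula is mmol/L = 10 × (mg/dL) / M.

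The plan's own cholesterol pair first, at an assumed M = 386.65: 3000 / 386.65 = 7.76 mmol/L, against 7.75 stated. That pair agrees within 0.2%, which suggests that the lipid pairs are meant as one limit in two units. It does not test the triglyceride pair, because a different analyte has a different conversion.

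Triglycerides:

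| Assumed M (g/mol) | 1.71 mmol/L in mg/dL (1.71 × M/10) | 300 mg/dL in mmol/L (3000/M) | Ratio of the two limits |
|---|---|---|---|
| 800 | 136.8 | 3.75 | 2.19 |
| 885.7 | 151.5 | 3.39 | 1.98 |
| 950 | 162.4 | 3.16 | 1.85 |

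For the two figures to agree, M would have to be 3000 / 1.71 = 1754 g/mol, about twice the central assumption. The band in which a patient passes one limit and fails the other runs from about 151 to 300 mg/dL (lower end 137 to 162 over the range).

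The effect depends on what *or* means:

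- either limit suffices: 300 mg/dL governs and the mmol/L figure does nothing;
- the reporting unit decides: the limit is 300 mg/dL for a laboratory reporting mg/dL, and about 151 mg/dL for one reporting mmol/L;
- both must hold: about 151 mg/dL governs everywhere.

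**3. INR.** Section 4.1.4 lists eight limits: neutrophils, hemoglobin, platelets, AST/ALT, bilirubin, eGFR, cholesterol and triglycerides. None is INR. The Study Calendar schedules no PT/INR test, and INR otherwise appears only in the Child-Pugh table (Appendix II).

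**4. Prostate cancer.** Section 4.2.6 uses a grade and 4.2.27 uses a risk category that the documents do not define for prostate cancer. A man with Gleason 6 disease on surveillance could be exempted by the first and excluded by the second.

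**5. Effect on the design.** Section 12.1 stops at 2 or fewer responses in 18 and rejects the null at 8 or more in 43. With 43 − 18 = 25 patients in stage II, the probability of rejection is the sum over x = 3 to 18 of P(X₁ = x) × P(X₂ ≥ 8 − x), where X₁ is binomial (18, p) and X₂ is binomial (25, p). This gives 0.048 at p = 10% and 0.800 at p = 25%. The probability of early stopping at p = 10% is 0.734. The stated 5%, 80% and 73% are reproduced, and none of them depends on the criteria above.

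**The case against.** The strongest reply on prior treatment is that a specific permission limits a general rule: 4.1.2 speaks of a different lesion, so 4.2.5 must mean the AML being enrolled. This is a sensible reading and may be what was intended. It defeats one inference that a reader might draw, namely that no eligibility checklist could satisfy both criteria. An item confined to the study lesion would satisfy both on this reading, and the checklist required by Section 4.4 is not in the documents. What remains is that 4.2.5 does not contain the limit.

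On triglycerides, the documents point to conduct in the United States: HIPAA consent, registration hours in EST, FDA reporting. If every laboratory reports mg/dL and the pair is read as one limit, 300 mg/dL governs and the disputed band is empty. That stands. Because every patient is tested, a reader might infer that the mismatch affects everyone's eligibility. The documents do not support this, since nothing in them shows that any laboratory reports mmol/L. The mismatch itself stands at every molar mass in the range.

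On prostate cancer, grade and risk category are different things. A reader might infer a contradiction, but the text shows only a probable overlap. It is also reasonable to let the specific 4.2.6 prevail over the general 4.2.1. The INR reference concerns only patients with a recently treated DVT.

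**Conclusion.** The point holds for two criteria and should be fixed.

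- Sections 4.1.2 and 4.2.5 conflict on the literal text. They can be harmonised only by a limit to the study lesion that 4.2.5 does not state.
- The triglyceride limit is wrong as written, because its two figures differ by a factor of 1.98 (1.85 to 2.19), given an assumed molar mass of 885.7 g/mol (950 to 800). It has practical effect only where mmol/L is reported or both limits must hold. The arithmetic does not show which figure was intended.

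The INR cross-reference leads nowhere, and with no PT/INR test on the calendar the note to 4.2.15 has neither a limit nor a scheduled measurement behind it. This and the undistinguished prostate terms are minor notes.

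The documents give no frequency for any of these groups, so the number of patients affected cannot be estimated. A reader might infer that the trial's error rates or analysis set are compromised. They are not: the design figures reproduce, and Section 3.0 defines the analysis set by receipt of one dose.

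**What to change.** - Reconcile 4.1.2 and 4.2.5 in a single statement on prior AML treatment that says which lesion or lesions it covers.
- State one triglyceride limit whose mg/dL and mmol/L values agree.
- Supply the INR criterion that 4.2.15 refers to, with a matching calendar entry, or remove the cross-reference.
- Use one defined term for the prostate cancers meant in 4.2.6 and 4.2.27, and say how it relates to 4.2.1.
- Update the eligibility checklist to match.

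The sponsor chooses the rules and limits. The cost is amendment wording and a revised checklist, plus a calendar line if an INR criterion is added. Design, sample size and analysis stay as they are.

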4.2. Exclusion Criteria

- 4.2.1 History of tuberous sclerosis, LAM or any active malignancy
- 4.2.2 Active treatment with any other investigational agents
- 4.2.3 Administration of any investigational drug within 30 days or 5 half-lives, whichever is longer, preceding the first dose of study treatment.
- 4.2.4 Concurrent therapy given to treat cancer
- 4.2.5 Patients must not have received any prior treatment for AML
- 4.2.6 Diagnosis of any other malignancy within 3 years prior to registration, except for adequately treated basal cell or squamous cell skin cancer, or carcinoma in situ of the breast or of the cervix or melanoma in-situ or low grade (Gleason 6 or below) prostate cancer on surveillance with no plans for treatment intervention (eg, surgery, radiation or castration).
- 4.2.7 Clinically significant gastrointestinal abnormalities that may increase the risk for gastrointestinal bleeding including, but not limited to:
- Active peptic ulcer disease
 - Inflammatory bowel disease (e.g. ulcerative colitis, Crohn's disease), or other gastrointestinal conditions with increased risk of perforation.
 - History of abdominal fistula, gastrointestinal perforation, or intra-abdominal abscess within 28 days prior to beginning study treatment
- 4.2.8 Active diarrhea of any grade.
- 4.2.9 Clinically significant gastrointestinal abnormalities that may affect absorption of investigational product including, but not limited to:
- Malabsorption syndrome
 - Major resection of the stomach or small bowel resulting in dumping syndrome or clinical signs of malabsorption

- 4.2.10 Active or prior history of human immunodeficiency virus (HIV), hepatitis B, or hepatitis C (screening for all three is mandatory prior to study)
- 4.2.11 Presence of any active or ongoing infection.
- 4.2.12 Any known uncontrolled underlying pulmonary disease by history, physical exam or if applicable PFTs (e.g. FEV1 or DLCO 50% or less of predicted OR O2 saturation 88% or less at rest on room air).
- 4.2.13 History of any one or more of the following cardiovascular conditions within the past 6 months:
- Cardiac angioplasty or stenting
 - Myocardial infarction
 - Unstable angina
 - Coronary artery bypass graft surgery
 - Symptomatic peripheral arterial vascular disease
- 4.2.14 History of Class III or IV congestive heart failure, as defined by the New York Heart Association Classification of Congestive Heart Failure. See Appendix I for NYHA Classification Table.
- 4.2.15 History of cerebrovascular accident including transient ischemic attack (TIA), pulmonary embolism or untreated deep venous thrombosis (DVT) within the past 6 months.
Note: Patients with recent DVT who have been treated with therapeutic anticoagulation agents for at least 6 weeks are eligible as long as their INR is stable and within inclusion criteria per 4.1.4
- 4.2.16 Corrected QT interval (QTc) > 480 milliseconds as corrected by the Fridericia formula
- 4.2.17 Poorly controlled hypertension, defined as systolic blood pressure (SBP) of ≥ 140 mmHg or diastolic blood pressure (DBP) of ≥ 90 mmHg.
Note: Screening/Baseline blood pressure (BP) must be assessed with three measurements at approximately 2-minute intervals. The mean SBP / DBP values from the three readings must be $< 140/90$ mmHg in order for a subject to be eligible for the study. If the subject's initial screening SBP/DBP is $\geq 140/90$ mmHg, initiation or adjustment of antihypertensive medication(s) is permitted in an attempt to control the subject's BP level to below $140/90$ mmHg. Optimal blood pressure control must be achieved before registration and monitored.
- 4.2.18 Evidence of active bleeding or bleeding diathesis
- 4.2.19 Patients must not have uncontrolled diabetes mellitus (defined by a Hgb A1c > 8) obtained within 14 days prior to registration. Optimal glucose control (Hgb A1c ≤ 8) must be achieved before registration and monitored during protocol treatment

- 4.2.20 Unable or unwilling to discontinue use of prohibited medications within 14 days prior to randomization and while on treatment:
- No chronic treatment with systemic steroids or another immunosuppressive agent. Topical or inhaled corticosteroids are allowed.
 - Growth factors (e.g. G-CSF, G-GM-CSF, erythropoietin, platelets growth factors etc.) are not to be administered prophylactically but may be prescribed by the treating physician for rescue from severe hematologic events.
 - Live vaccines must not be administered to patient due to immunosuppressant potential of everolimus.
 - Drugs known to be strong inhibitors or inducers of CYP3A4 must not be administered. Drugs or substances known to be moderate inhibitors or inducers of CYP3A should be avoided if possible or used subject to caution as these can alter everolimus metabolism. Co-administration with strong or moderate inhibitors of P-glycoprotein (PgP) should be avoided if possible, or used subject to caution Seville orange, star fruit, grapefruit and their juices affect P450 and PgP activity. Concomitant use should be avoided.
- 4.2.21 Have a known immediate or delayed hypersensitivity reaction or idiosyncrasy to drugs chemically related to everolimus that in the opinion of the investigator contraindicates their participation.
- 4.2.22 Prior or current use of systemic anti-VEGF inhibitors, cytokines or mTOR inhibitors (e.g. interferon, interleukin 2).
- 4.2.23 Patients with Child-Pugh A-C liver disease (See Appendix II: Child-Pugh Criteria)
- 4.2.24 Pregnant or nursing (lactating) women
- 4.2.25 Women of child-bearing potential (WOCBP), defined as all women physiologically capable of becoming pregnant, must use highly effective methods of contraception during the study and 8 weeks after stopping treatment. Highly effective contraception methods include total abstinence, male partner sterilization (with post-vasectomy documentation of the absence of sperm in the ejaculate), or a combination of **any two** of the following:
- Use of oral, injected or implanted hormonal methods of contraception
 - In case of use of oral contraception, women should have been stable on the oral agent before taking study treatment.
 - Placement of an intrauterine device (IUD) or intrauterine system (IUS)
 - Barrier methods of contraception: condom or occlusive cap (diaphragm or cervical/vault caps) with spermicidal foam/gel/film/cream/ vaginal suppository

Women are considered to be physiologically capable of becoming pregnant unless:

- They have had 12 months of natural (spontaneous) amenorrhea with an appropriate clinical profile (e.g. age appropriate, history of vasomotor symptoms);
- They have had surgical bilateral oophorectomy (with or without hysterectomy) or tubal ligation at least six weeks prior to randomization.
 - In the case of oophorectomy alone, only when the reproductive status of the woman has been confirmed by follow up hormone level assessment is she considered not of child-bearing potential.

4.2.26 Male patients whose sexual partner(s) are WOCBP must agree to use adequate contraception as defined above during the study and for 8 weeks after the end of treatment. Condom use is required by all male patients in order to prevent delivery of the drug via seminal fluid.

4.2.27 Any serious and/or unstable pre-existing medical, psychiatric, or other condition that could interfere with subject's safety, provision of informed consent, or compliance to study procedures. Patients with low risk prostate and bladder cancer will be excluded (use AUA guidelines for bladder patients).

